14.1. Schedule of Activities (SoA)

Cohorts 1 to 3

	Screening Day -28 to Day -2	Day -1	Day 1	Day 2	Day 3	Follow-up Visit ^a (14 days post-dose)
Informed consent	X					
Inclusion/exclusion criteria	X	X	X			
Demographic data	X					
Medical history	X					
Urinary drug screen	X	X				
Alcohol screen	X	X				
Testing for HIV, hepatitis B and C	X					
Pregnancy testing ^b	X	X				
FSH testing in women	X					
Randomization				X		
Admission to CRU		X				
Discharge from CRU						X
Height, body weight, and BMI ^c	X	X			X	X
Study drug administration			X			
Adverse event recording	X	X	X	X	X	X
Blood pressure, temperature, respiratory rate, and pulse rate	X	X	X ^d	X	X	X
12-lead paper safety ECG	X	X	X ^e	X ^e	X ^e	
12-lead digital ECG			X ^e	X ^e	X ^e	
Telemetry ^f		X	X			
Clinical laboratory evaluations ^g	X	X		X		X
Physical examination	X	X			X	X
Blood sampling for PK ^h			X	X	X	

^a Tests will be performed at follow-up and also in cases of discontinuation.

^b Serum pregnancy test will be performed at screening and check-in.

^c Height will be measured at screening only.

^d Blood pressure, temperature, respiratory rate, and pulse rate will be measured at pre-dose, then at 1, 2, 3, 4, 6, 8, 12, 24, and 48 hours post-dose.

^e Paper and digital ECGs will be collected at the same time points as PK sampling. Recording of ECGs will precede PK sampling and check of vital signs at each time point.

- f Telemetry for 4 to 6 hours on Day -1 to establish a baseline. Pre-dose to 24 hours post-dose.
- g Clinical laboratory assessments must be repeated if first collected more than 2 weeks before dosing.
- h Blood samples will be collected at pre-dose, then at 0.25, 0.5, 1, 1.5, 2, 3, 4, 6, 8, 12, 24, 36, and 48 hours.

BMI body mass index; CRU Clinical Research Unit; ECG electrocardiogram; FSH follicle stimulating hormone; HIV human immunodeficiency virus; PK pharmacokinetic(s)

Cohorts 4 to 6

	Screening Day -28 to Day -2	Day -2	Day -1	Day 1	Day 2	Day 3	Day 4	Follow- up Visit ^a (14 days post-dose)
Informed consent	X							
Inclusion/exclusion criteria	X		X	X				
Demographic data	X							
Medical history	X							
Urinary drug screen	X		X					
Alcohol screen	X		X					
Testing for HIV, hepatitis B and C		X						
Pregnancy testing ^b	X		X					
FSH testing in women	X							
Randomization				X				
Admission to CRU		X						
Discharge from CRU							X	
Height, body weight, and BMI ^c	X		X				X	X
Study drug administration				X				
Adverse event recording	X	X	X	X	X	X	X	X
Blood pressure, temperature, respiratory rate, and pulse rate	X		X	X ^d	X	X	X	X
12-lead paper safety ECG	X		X	X ^e	X ^e	X ^e	X ^e	
12-lead digital ECG				X ^e	X ^e	X ^e	X ^e	
Telemetry ^f			X	X				
Clinical laboratory evaluations ^g	X		X		X			X
Physical examination	X		X				X	X
Blood sampling for PK ^h				X	X	X	X	
Blood sampling for testosterone, LH, FSH, and inhibin B (male subjects only) ⁱ			X	X	X	X	X	

^a Tests will be performed at follow-up and also in cases of discontinuation.

^b Serum pregnancy test will be performed at screening and check-in.

- c Height will be measured at screening only.
- d Blood pressure, temperature, respiratory rate, and pulse rate will be measured at pre-dose, then at 1, 2, 3, 4, 6, 8, 12, 24, and 48 hours post-dose.
- e Paper and digital ECGs will be collected at the same time points as PK sampling. Recording of ECGs will precede PK sampling and check of vital signs at each time point.
- f Telemetry for 4 to 6 hours on Day -1 to establish a baseline. Pre-dose to 24 hours post-dose.
- g Clinical laboratory assessments must be repeated if first collected more than 2 weeks before dosing.
- h Blood samples will be collected at pre-dose, then at 0.25, 0.5, 1, 1.5, 2, 3, 4, 6, 8, 12, 24, 36, 48, and 72 hours.
- i Male subjects only: samples for testosterone, LH, FSH, and inhibin B will be collected at 0 hour (0800 or 1000) and at 4, 6, 8, 12, 22, and 24 hours on Day -1 and at 0 hour (0800 or 1000) and at 1, 2, 4, 6, 8, 12, 24, 36, 48, and 72 hours on Day 1 to Day 3. The '0' hour time point should be approximately the same time that dosing is scheduled for on Day 1. On Day 1, samples for testosterone, LH, FSH, and inhibin B will be collected at the same time as PK samples.

BMI body mass index; CRU Clinical Research Unit; ECG electrocardiogram; FSH follicle stimulating hormone; HIV human immunodeficiency virus; LH luteinizing hormone; PK pharmacokinetic(s)

14.2. Potential Clinically Significant (PCS) Laboratory Values

a). Hematology:

Parameter	Conventional Unit	Low PCS Criteria	High PCS Criteria	SI Unit	Low PCS Criteria	High PCS Criteria
Hematocrit	%	< 30	> 50 (F) > 55 (M)	L/L	< 0.3	> 0.5 (F) > 0.55 (M)
Hemoglobin (male)	g/dL	< 11	> 18	g/L	110	180
Hemoglobin (female)	g/dL	< 10	> 17	g/L	100	170
Leukocyte (White Blood Cell Count)	$10^3/\mu\text{L}$	≤ 2.8	≥ 15	$10^9/\text{L}$	≤ 2.8	≥ 15
Neutrophils	cells/ mm^3	1500	No upper limit	Proportion of 1.0	≤ 0.15	No upper limit
Platelet Count	$10^3/\mu\text{L}$	≤ 75	≥ 700	$10^9/\text{L}$	≤ 75	≥ 700

PCS = potentially clinically significant; SI = *Le Système International d'Unités* (International System of Units).

b). Chemistry:

Parameter	Conventional Unit	Low PCS Criteria	High PCS Criteria	SI Unit	PCS Low Limit	PCS High Limit
Alanine aminotransferase	U/L	No lower limit	$\geq 3 \times \text{ULN}$	U/L	No lower limit	$\geq 3 \times \text{ULN}$
Aspartate aminotransferase	U/L	No lower limit	$\geq 3 \times \text{ULN}$	U/L	No lower limit	$\geq 3 \times \text{ULN}$
Albumin	g/dL	≤ 2.6	≥ 6.0	g/L	≤ 26	≥ 60
Alkaline phosphatase	U/L	No lower limit	$\geq 3 \times \text{ULN}$	U/L	No lower limit	$\geq 3 \times \text{ULN}$
Bilirubin, total	mg/dL	No lower limit	$\geq 1.5 \times \text{ULN}$	$\mu\text{mol/L}$	No lower limit	$\geq 1.5 \times \text{ULN}$
Blood urea nitrogen	mg/dL	No lower limit	≥ 30.0	mmol/L	No lower limit	≥ 10.71
Creatinine Kinase (CK)	U/L	No lower limit	$\geq 3 \times \text{ULN}$	U/L	No lower limit	$\geq 3 \times \text{ULN}$
Calcium, total	mg/dL	< 8.0	> 11.0	mmol/L	< 2.0	> 2.75
Chloride	mEq/L	≤ 85	≥ 120	mmol/L	≤ 85	≥ 120
Glucose	mg/dL	≤ 45.1	≥ 200.0	mmol/L	≤ 2.48	≥ 11
Gamma Glutamyl Transferase (GGT)	U/L	NA	$\geq 3 \times \text{ULN}$	U/L	No lower limit	$\geq 3 \times \text{ULN}$
Lactate Dehydrogenase (LDH)	U/L	No lower limit	$\geq 3 \times \text{ULN}$	U/L	No lower limit	$\geq 3 \times \text{ULN}$
Potassium	mEq/L	≤ 3.0	≥ 5.5	mmol/L	≤ 3.0	≥ 5.5
Protein, total	g/dL	≤ 5.0	≥ 10.0	g/L	≤ 50	≥ 100
Sodium	mEq/L	≤ 125	≥ 155	mmol/L	≤ 125	≥ 155
Serum Creatinine	mg/dL	No lower limit	$> 1.5 \times \text{ULN}$	$\mu\text{mol/L}$	No lower limit	$> 1.5 \times \text{ULN}$
Triglycerides	mg/dL	No lower limit	> 300	mmol/L	No lower limit	> 3.39
TSH	$\mu\text{U/L}$	below normal range	above normal range	mIU/L	below normal range	above normal range
T4, free	ng/dL	below normal range	above normal range	pmol/L	below normal range	above normal range

Parameter	Conventional Unit	Low PCS Criteria	High PCS Criteria	SI Unit	PCS Low Limit	PCS High Limit
Uric acid (Male)	mg/dL	No lower limit	≥ 10.5	$\mu\text{mol}/\text{L}$	No lower limit	≥ 624.75
Uric acid (Female)	mg/dL	No lower limit	≥ 8.5	$\mu\text{mol}/\text{L}$	No lower limit	≥ 505.75

PCS = potentially clinically significant; SI = *Le Système International d'Unités* (International System of Units); ULN = upper limit of normal (value provided by the laboratory).

c). Urinalysis:

Parameter	PCS Low Limit	PCS High Limit
Hb/RBCs/Blood	NA	$\geq +2$
Protein/Albumin	NA	$\geq +2$
Glucose	NA	$\geq +2$

NA = Not Available.

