8.2.1 Clinical safety laboratory assessments

The clinical chemistry, hematology, and urinalysis will be performed at a local laboratory at or near to the study site.

See [Table 11](#) for the list of clinical safety laboratory tests to be performed and to the SoA ([Table 1](#) and [Table 2](#)) for the timing and frequency. All CSP-required laboratory assessments, as defined in the table, must be conducted in accordance with the laboratory manual and the SoA ([Table 1](#) and [Table 2](#)).

The Investigator should make an assessment of the available results with regard to clinically relevant abnormalities. The laboratory results should be signed, dated, and retained at center as source data for laboratory variables.

For information on how AEs based on laboratory tests should be recorded and reported, see [Section 8.3.7](#).

Additional safety samples may be collected and analyzed if clinically indicated at the discretion of the Investigator. The date of collection will be recorded on the appropriate CRF.

Table 11 Laboratory safety variables

Hematology (whole blood)	Clinical Chemistry (serum or plasma)
White blood cell (WBC) count	Alanine aminotransferase (ALT)
Red blood cell (RBC) count	Aspartate aminotransferase (AST)
Hemoglobin (Hb)	Alkaline phosphatase (ALP)
Hematocrit (HCT)	Gamma glutamyl transpeptidase (GGT)
Mean corpuscular volume (MCV)	Total bilirubin
Mean corpuscular hemoglobin (MCH)	Unconjugated bilirubin
Mean corpuscular hemoglobin concentration (MCHC)	C-reactive protein (CRP)
Neutrophils absolute count	Blood Urea Nitrogen
Monocytes absolute count	Creatinine
Eosinophils absolute count	Glucose (fasting)
Basophils absolute count	Albumin
Platelets	Phosphate
Reticulocytes absolute count	Potassium Calcium
Urinalysis	
Glucose	Bicarbonate
Protein	Thyroid stimulating hormone (TSH) ^a
Hemoglobin	Thyroxine (T ₄) ^b
Microscopy (if positive for blood or protein)	Follicle stimulating hormone (FSH) ^c
Viral serology	
Human immunodeficiency virus (HIV I and II)	Human beta chorionic gonadotrophin
Hepatitis B surface antigen (HBsAg)	
Hepatitis C Virus antibody	

^a Screening only

^b Reflex only (if TSH is abnormal)

^c Screening for post-menopausal women

NB. In case a subject shows an AST **or** ALT $\geq 3 \times \text{ULN}$ together with total bilirubin $\geq 2 \times \text{ULN}$ refer to [Appendix C](#) 'Actions required in cases of increases in liver biochemistry and evaluation of Hy's Law', for further instructions

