9.4.2.1 Safety and tolerability

Adverse events will be listed and summarized by Medical Dictionary for Regulatory Activities system organ class and preferred term, and by treatment regimen. The presentation period of AEs will be the time from first dose to follow-up.

Vital signs, body temperature, body weight and BMI, clinical laboratory measures, and dECG interval data will be summarized using descriptive statistics by treatment regimen and CSP time (eg, visit number, date, and time).

Individual data for vital signs, body weight and BMI, clinical laboratory measures, dECG intervals, overall pECG assessments (made by the Investigator), and physical examination results will be flagged and listed for any potentially clinically important (PCI) values for each subject according to predetermined PCI criteria.

Project-specific reference limits will be used in the statistical analysis. When project-specific reference limits are not available, the reference limits of the local laboratory will be used.

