8.3. Clinical Laboratory Evaluations

The clinical chemistry, hematology, and urinalysis will be performed at visits specified in Appendix 14.1 SoA.

Other laboratory tests include testing for immunodeficiency virus (HIV), hepatitis B and C at screening, urine drug screen and alcohol screen at screening and on Day -1, pregnancy test at screening and on Day -1, and follicle stimulating hormone (FSH) testing in women at screening.

The details of clinical laboratory assessments to be performed are listed in Table 8-1.

Table 8-1 Laboratory Safety Variables

Hematology (whole blood)	White blood cell (WBC) count, red blood cell (RBC) count, hemoglobin (Hb), hematocrit (HCT), mean corpuscular volume (MCV), mean corpuscular hemoglobin (MCH), mean corpuscular hemoglobin concentration (MCHC), neutrophils absolute count, monocytes absolute count, eosinophils absolute count, basophils absolute count, platelets, and reticulocytes absolute count
Clinical chemistry (serum or plasma)	Alanine aminotransferase (ALT), aspartate aminotransferase (AST), alkaline phosphatase (ALP), gamma glutamyl transpeptidase (GGT), total bilirubin, unconjugated bilirubin, C-reactive protein (CRP), blood urea nitrogen, creatinine, glucose (fasting), albumin, phosphate, potassium, calcium, sodium, bicarbonate, thyroid stimulating hormone (TSH) ^a , thyroxine (T ₄) ^b , and follicle stimulating hormone (FSH) ^c
Urinalysis	Glucose, protein, hemoglobin, microscopy (if positive for blood or protein)
Viral serology	Human immunodeficiency virus (HIV I and II), hepatitis B surface antigen (HBsAg) and hepatitis C Virus antibody
Pregnancy test (females only)	Human beta chorionic gonadotrophin
Urine drug screen	Alcohol and cotinine, amphetamines (includes methamphetamine and ecstasy/3,4 methylenedioxymethamphetamine), barbiturates, benzodiazepines, cannabinoids (includes tetrahydrocannabinol), cocaine metabolites, methadone, tricyclic antidepressants, opiates (includes heroin, codeine, and oxycodone), and phencyclidine.

a Screening only

b Reflex only (if TSH is abnormal)

c Screening for post-menopausal women

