The clinical laboratory that will perform the tests will provide the reference ranges for all clinical laboratory parameters. Abnormal clinical laboratory values will be flagged as either high or low (or normal or abnormal) based on the reference ranges for each laboratory parameter and evaluated as clinically significant or not clinically significant by the investigator. All laboratory results along with the abnormal flag and clinical significance will be presented in data listings. The potentially clinically significant (PCS) values will also be flagged. The PCS criteria are defined in Appendix 14.2.

Actual results and changes from baseline will be summarized for hematology, chemistry, quantitative urinalysis laboratory tests by treatment and visit. Shift tables with categories of low, normal, and high for quantitative results, and normal and abnormal for qualitative results will be provided by treatment and visit.

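### SAP 14.2 states the low neutrophil PCS limit as two quantities that do not convert into each other: 1500 cells/mm3 and a proportion of 0.15 or below

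*SAP*

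**What the plan says.** Protocol 9.4.2.1 commits to having individual laboratory data "flagged and listed for any potentially clinically important (PCI) values for each subject according to predetermined PCI criteria". SAP 8.3 takes this up: "The potentially clinically significant (PCS) values will also be flagged", and "The PCS criteria are defined in Appendix 14.2".

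The hematology part of Appendix 14.2 has a conventional-unit block and an SI block, each with a low and a high limit. In the neutrophil row:

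- Conventional block: unit cells/mm3, low limit 1500, no upper limit.
- SI block: unit "Proportion of 1.0", low limit 0.15 or below, no upper limit.

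The variable to be collected is listed as "Neutrophils absolute count" in Protocol Table 11 (section 8.2.1) and as "neutrophils absolute count" in SAP Table 8-1 (section 8.3). Neither table lists a neutrophil percentage or proportion.

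**The concern.** A table with two unit systems should state one criterion twice, so that the same sample is flagged whichever units the listing uses. For neutrophils it does not. A count can be turned into a proportion only by dividing by that sample's WBC, so the two entries are separate rules that can disagree on the same blood sample. SAP 8.3 names no governing column and specifies no derivation of neutrophils divided by WBC.

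The stakes are small but real. Safety is a primary objective. Protocol 8.3.7 limits when a worsening of a protocol-mandated laboratory value is reported as an adverse event, and the shift tables use only low, normal and high. Among the planned laboratory outputs, the PCS flag is the prespecified numeric threshold beyond the reference range. For this analyte, whether it appears could depend on which column is programmed.

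**Working it through.** **Inputs, all from SAP 14.2 unless stated.** Low neutrophil limit 1500 cells/mm3 (conventional) and 0.15 (SI, as a proportion). Leukocyte PCS limits 2.8 and 15 x 10^9/L, used only to bound the WBC range. The WBC values inside that range are illustrative; the documents give no WBC distribution.

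**Step 1. Convert the conventional limit.** 1500 cells/mm3 x 10^6 mm3/L = 1.5 x 10^9/L. The SI entry of 0.15 is not reproduced, and its stated unit is not a concentration.

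**Step 2. Find where the limits coincide.** 0.15 x WBC = 1500 gives WBC = 1500 / 0.15 = 10,000/mm3, and nowhere else.

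**Step 3. Express each limit in the other's terms.**

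| WBC (/mm3) | 0.15 x WBC (cells/mm3) | 1500 / WBC |
|---|---|---|
| 2,800 | 420 | 0.536 |
| 4,000 | 600 | 0.375 |
| 5,000 | 750 | 0.300 |
| 8,000 | 1,200 | 0.188 |
| 10,000 | 1,500 | 0.150 |
| 12,000 | 1,800 | 0.125 |
| 15,000 | 2,250 | 0.100 |

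Below a WBC of 10,000 the proportion is the laxer rule; above it, the stricter.

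**Step 4. Discordant samples.**

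- WBC 5,000 and neutrophils 1,200: proportion 1,200 / 5,000 = 0.24. Flagged by the count, not by the proportion. The same holds for any count between 750 and 1,500 at this WBC.
- WBC 12,000 and neutrophils 1,700: proportion 1,700 / 12,000 = 0.142. Flagged by the proportion, not by the count. The same holds for any count between 1,500 and 1,800 at this WBC.

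**Step 5. Check how the rest of the table behaves.** SI limit divided by conventional limit, for the other rows with numbers in both blocks:

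- Hematology (5 rows): hematocrit 0.01; hemoglobin, male and female, 10; leukocytes 1; platelets 1.
- Chemistry (11 rows): albumin 10; blood urea nitrogen 10.71/30 = 0.357; calcium 0.25; chloride 1; glucose 2.48/45.1 = 0.055 and 11/200 = 0.055; potassium 1; total protein 10; sodium 1; triglycerides 3.39/300 = 0.0113; uric acid 624.75/10.5 = 59.5 (male) and 505.75/8.5 = 59.5 (female).

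That is 16 rows and 29 limits, each with a fixed factor. The blocks are therefore meant as one criterion in two unit systems, and neutrophils is the only exception.

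**The case against.** The strongest reply is that the ambiguity is mostly nominal. Only an absolute count is collected, so only the 1500 entry can be applied without a derivation that the SAP does not specify. Appendix 14.2 also looks like a generic list: it has limits for creatine kinase, lactate dehydrogenase, triglycerides and uric acid, none of which is in SAP Table 8-1. Entries with no matching variable simply do nothing, and the proportion could be one of them. Further, SAP 8.3 flags every value against the laboratory's reference range, has the investigator judge clinical significance, and lists all results, so no neutrophil value is hidden. The subjects are healthy volunteers, screened for clinically important hematology abnormalities (Protocol 5.2) and given one dose, and nothing shows that any sample would fall in a discordant zone.

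Most of this stands and keeps the point small. The count is probably what was intended. It does not remove the fault. Unlike an unmatched analyte, the neutrophil entry belongs to a variable that is collected, and a listing prepared in SI units would look to that column. There it would find either a limit that cannot be applied to a count or, after dividing by WBC, one worth 600 to 750 cells/mm3 at WBC 4,000 to 5,000. A likely choice by the programmer is not a prespecified one.

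**Conclusion.** The concern holds. The neutrophil row gives two non-equivalent low limits, and the SAP does not say which applies. This is not a text-extraction fault: the unit label is legible and 0.15 is consistent with it.

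The consequence is confined to the neutrophil PCS flag in the data listings. The summaries, shift tables and reference-range flags in SAP 8.3 and the dose-escalation criteria in Protocol 7.1 do not use this limit. The size of the disagreement rests on the illustrative WBC values above, and no number of affected subjects can be given. The absence of a comparison sign beside 1500 carries no weight, because it may have been lost when the PDF was read; the hemoglobin SI limits also show none.

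**What to change.** Reconcile the neutrophil row of SAP 14.2 so that both unit columns express the same absolute-count limit with the same comparison operator. As a conversion of the SAP's own figure, 1500 cells/mm3 is 1.5 x 10^9/L, the SI unit the table already uses for leukocytes and platelets. The sponsor should confirm the intended limit and check the operator against the source file.

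The cost is one corrected row in a SAP appendix. It needs no protocol amendment, extra sample or new analysis.

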14.3. Potential Clinically Significant (PCS) Vital Sign Values

Parameter	Unit	Observed Value	And/Or	Change from Baseline	Change from Supine to Standing	Flag
Systolic Blood Pressure (supine or sitting)	mmHg	≥ 180	And	Increase of ≥ 20 mmHg	--	PCS High
		≤ 90	And	Decrease of ≥ 20 mmHg	--	PCS Low
Diastolic Blood Pressure (supine or sitting)	mmHg	≥ 105	And	Increase of ≥ 15 mmHg	--	PCS High
		≤ 50	And	Decrease of ≥ 15 mmHg	--	PCS Low
Pulse (supine or sitting)	bpm	≥ 120	And	Increase of ≥ 15 bpm	--	PCS High
		≤ 50	And	Decrease of ≥ 15 bpm	--	PCS Low
Systolic Blood Pressure (supine to standing)	mmHg	≤ 80	And	--	Decrease of ≥ 20	PCS Low
Diastolic Blood Pressure (supine to standing)	mmHg	--	--	--	Decrease of ≥ 20	PCS Low
Weight	Not Applicable			Increase of ≥ 7%	--	PCS High
				Decrease of ≥ 7%	--	PCS Low

PCS = potentially clinically significant.
